10.9 Appendix 9: Calculation of Creatinine Clearance

Cockcroft-Gault equations for participants ≥ 18 years old:

- If male:

$$\text{CrCL (mL/min)} = \frac{(140 - \text{age [y]}) \times \text{weight [kg]}}{72 \times \text{serum creatinine (mg/dL)}}$$

- If female:

$$\text{CrCL (mL/min)} = \frac{(140 - \text{age [y]}) \times \text{weight [kg]} \times 0.85}{72 \times \text{serum creatinine (mg/dL)}}$$

10.10 Appendix 10: Abbreviations

Abbreviation	Expanded Term
3TC	lamivudine
ABC	abacavir
ADME	absorption, distribution, metabolism, and excretion
AE	adverse event
ALT	alanine aminotransferase
APaT	All-Participants-as-Treated
ART	antiretroviral therapy
AST	aspartate aminotransferase
AUC _{0-last}	area under the concentration-time curve from dosing to the time of the last measured concentration
AZT	azidothymidine
BSEP	bile salt export pump
C ₁₆₈	concentration at 168 hours
CDC	Centers for Disease Control and Prevention
CG	Cockcroft-Gault
CI	confidence interval
C _{max}	maximum plasma concentration
CNS	central nervous system
CONSORT	Consolidated Standards of Reporting Trials
COVID-19	coronavirus disease caused by the SARS-CoV-2 virus
CrCl	creatinine clearance
CRF	Case Report Form
CSR	Clinical Study Report
CT	chlamydia trachomatis
CTFG	Clinical Trial Facilitation Group
C _{trough}	concentration reached by a drug immediately before the next dose is administered
CYP	cytochrome P450
DAIDS	Division of AIDS
DDI	drug-drug interaction

Abbreviation	Expanded Term
DILI	drug-induced liver injury
DMC	Data Monitoring Committee
DNA	deoxyribonucleic acid
DP	diphosphate
ECG	electrocardiogram
ECI	event of clinical interest
eCRF	electronic Case Report Form
EDC	electronic data collection
EEA	European Economic Area
EFV	efavirenz
EMA	European Medicines Agency
EOC	Executive Oversight Committee
EOT	End of Treatment
FBR	future biomedical research
FDA	Food and Drug Administration
FDAAA	Food and Drug Administration Amendments Act
FSH	follicle stimulating hormone
FTC	emtricitabine
GC	Neisseria gonorrhoeae
GCP	Good Clinical Practice
GCV	geometric coefficient of variation
GERD	gastroesophageal reflux disease
HBcAb	hepatitis B core antibody
HBsAg	hepatitis B surface antigen
HBV	hepatitis B virus
hCG	human chorionic gonadotropin
HCV	hepatitis C virus
HIV	human immunodeficiency virus
HIV-1	human immunodeficiency virus type 1
HIV-2	human immunodeficiency virus type 2

Abbreviation	Expanded Term
HRT	hormone replacement therapy
IA(s)	interim analysis(ses)
IB	Investigator's Brochure
IC ₅₀	concentration of a drug or inhibitor needed to inhibit a biological process or response by 50%
ICF	informed consent form
ICH	International Council for Harmonisation of Technical Requirements for Pharmaceuticals for Human Use
ICMJE	International Committee of Medical Journal Editors
IEC	Independent Ethics Committee
IM	intramuscular
IMP	Investigational Medicinal Product
IND	Investigational New Drug
IQ	inhibitory quotient
IRB	Institutional Review Board
IRT	interactive response technology
ISL	islatravir, MK-8591
IUD	intrauterine device
IUS	intrauterine hormone-releasing system
JRCT	Japan Registry of Clinical Trials
M&N	Miettinen & Nurminen method
MP	monophosphate
NCT	Clinicaltrials.gov identifier
NDA	New Drug Application
NNRTI	non- nucleoside reverse transcriptase inhibitor
NRTI	nucleoside reverse transcriptase inhibitor
OAT1	organic anion transporter 1
OAT3	organic anion transporter 3
OATP1B1	organic anion transporting polypeptide 1B1
OCT2	organic cation transporter 2
PBMC	peripheral blood mononuclear cell

Abbreviation	Expanded Term
PCR	polymerase chain reaction
PEP	post-exposure prophylaxis
P-gp	p-glycoprotein
PK	pharmacokinetic(s)
POCBP	participant of childbearing potential
PONCBP	participant of nonchildbearing potential
PrEP	pre-exposure prophylaxis
QM	once monthly
QTc	QT interval corrected for heart rate
QTcF	QT interval corrected for heart rate by Fridericia's formula
RNA	ribonucleic acid
RT	reverse transcriptase
SAC	Scientific Advisory Committee
SAE	serious adverse event
SAP	Statistical Analysis Plan
SD	standard deviation
SGOT	serum glutamic oxaloacetic transaminase
SGPT	serum glutamic pyruvic transaminase
siIDMC	Standing Internal Data Monitoring Committee
SLAB	supplemental laboratory test(s)
SoA	schedule of activities
SOC	standard of care
SOP	Standard Operating Procedures
sSAP	supplemental Statistical Analysis Plan
STI	sexually transmitted infection
SUSAR	suspected unexpected serious adverse reaction
t _{1/2}	half-life
TAF	tenofovir alafenamide
TBNK	T- and B-lymphocyte and natural killer cell
TDF	tenofovir disoproxil

Abbreviation	Expanded Term
TFV	tenofovir
TP	triphosphate
ULN	upper limit of normal
US	United States
UTN	Universal Trial Number
VAMS	volumetric absorptive microsampling
WBC	white blood cell
WHO	World Health Organization
ZDV	zidovudine

## 1 INTRODUCTION

The SAP is a companion document to the protocol. While Section 9 of the protocol provides the principal features of the confirmatory analyses for this study, this SAP provides additional statistical analysis details/data derivations and may document modifications or additions to the protocol-specified analysis plan that are not principal in nature and/or result from information that was not available at the time of protocol finalization.

## 2 SUMMARY OF CHANGES

SAP Version #	SAP Section # and Name	Description of Change	Brief Rationale
Amendment 01	3.5.1 Statistical Methods for Safety Analyses	Added details about handling of missing data in safety analyses	To add clarity on how missing data points are treated in the analysis.
Amendment 02	3.1 Responsibility for Analyses/In-house Blinding	Updated the timing of Sponsor being unblinded.	To enable strategic decision making by the Sponsor.

## 3 ANALYTICAL AND METHODOLOGICAL DETAILS

This section outlines the principal statistical analysis strategy and procedures for the study. Changes to analyses made after the protocol has been finalized, but prior to unblinding, will be documented in an amendment of the SAP and referenced in the CSR for the study. Post hoc exploratory analyses will be clearly identified in the CSR.

### 3.1 Responsibility for Analyses/In-house Blinding

The statistical analysis of the data obtained from this study will be the responsibility of the Clinical Biostatistics department of the Sponsor.

This study will be conducted as a double-blind study under in-house blinding procedures. To allow programmatic decisions, there will be an unblinded Sponsor team to review data on an ongoing basis for the duration of the study. The official, final database will not be locked until medical/scientific review has been performed, protocol deviations have been identified, and data have been declared final and complete. The detailed list of unblinded Sponsor team is presented in section 6.3.3 of the protocol. All Sponsor personnel except for a blinded medical monitoring team will be unblinded after the last expected Follow-up Week 4 visit.

The Clinical Biostatistics department of the Sponsor will generate the randomized allocation schedule for study treatment assignment.

### **3.2 Hypotheses/Estimation**

There are no hypotheses to be tested in this study. Objectives of the study are stated in Section 3 of the protocol.

### **3.3 Analysis Endpoints**

Safety and PK endpoints that will be evaluated for within- and between-treatment differences are listed below.

#### **3.3.1 Safety Endpoints**

The primary safety assessment will include all accumulated safety data through the last follow-up visit. AEs leading to discontinuation from study intervention are assessed until Week 20 (last dose received). Safety and tolerability will be assessed by clinical review of all relevant parameters including AEs and laboratory test results.

#### **3.3.2 Pharmacokinetics Endpoints**

The secondary PK endpoints for the study are MK-8527 AUC0-last and Cmax.

Exploratory PK endpoints are:

- PBMC MK-8527-MP, MK-8527-DP, and MK-8527-TP: AUC0-last, Cmax, Ctrough, concentrations at common time points
- MK-8527-TP AUC0-last, Ctrough, Cmax, and t1/2

### **3.4 Analysis Populations**

#### **3.4.1 Safety Analysis Population**

Safety Analyses will be conducted in the APaT population, which consists of all randomized participants who received at least one dose of study intervention. Participants will be included in the treatment group corresponding to the study intervention they actually received for the analysis of safety data using the APaT population. This will generally be the treatment group to which they are randomized except for participants who take incorrect study intervention for the entire treatment period; such participants will be included in the treatment group corresponding to the study intervention actually received.

Analyses of laboratory test results will include only participants with at least one measurement obtained after at least one dose of study intervention. If the analysis will assess change from baseline, a baseline measurement is also required.

### **3.4.2 PK Analysis Population**

The PK analysis population consists of the subset of participants who comply with the protocol sufficiently to ensure that generated data will be likely to exhibit the effects of treatment, according to the underlying scientific model. Any participants or data values excluded from analysis will be identified, along with their reason for exclusion, in the CSR.

## **3.5 Statistical Methods**

### **3.5.1 Statistical Methods for Safety Analyses**

Safety and tolerability will be assessed by clinical review of AEs and other relevant parameters, including laboratory test results.

Safety analyses will be performed for the following between-group comparisons:

- MK-8527 (3 mg) vs placebo
- MK-8527 (6 mg) vs placebo
- MK-8527 (12 mg) vs placebo

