MK-8527 is in the same antiretroviral class as ISL (MK-8591), an NRTI currently in development for the treatment of HIV-1 infection. Exposure/dose-dependent decreases in total lymphocyte and lymphocyte subset counts were observed in clinical studies with ISL. The risk of lymphocyte decreases for MK-8527 at the proposed doses is considered low based on available nonclinical and clinical data. In 3 completed Phase 1 studies, no AEs associated with lymphocyte reductions were observed, and mean lymphocyte counts were unchanged in both the single- and multiple-ascending dose studies. In the present study, hematology (including lymphocyte subsets) will be closely monitored; participants who meet predefined discontinuation criteria for total lymphocyte and CD4+ T-cell counts will be discontinued from study intervention.

Additional details regarding specific benefits and risks for participants participating in this clinical study may be found in the accompanying IB and informed consent documents.

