3 HYPOTHESES, OBJECTIVES, AND ENDPOINTS

There are no hypotheses to be tested in this study.

The following objectives will be evaluated in adults at low-risk of human immunodeficiency virus type 1 (HIV-1) infection.

Primary Objective	Primary Endpoint
To evaluate the safety and tolerability of MK-8527 once monthly (3 mg, 6 mg, and 12 mg) during treatment and through the last follow-up visit.	Adverse events Adverse events leading to discontinuation of study intervention
Secondary Objective	Secondary Endpoint
To characterize the plasma pharmacokinetic profile of MK-8527 once monthly (3 mg, 6 mg, and 12 mg).	MK-8527 AUC _{0-last} and C _{max}
Tertiary/Exploratory Objectives	Tertiary/Exploratory Endpoints
To explore a relationship between intracellular MK-8527-MP, MK-8527-DP, and MK-8527-TP: AUC _{0-last} , C _{max} , C _{trough} , concentrations at common time points	PBMC MK-8527-MP, MK-8527-DP, and MK-8527-TP: AUC _{0-last} , C _{max} , C _{trough} , concentrations at common time points
To characterize the intracellular pharmacokinetic profile of MK-8527-TP in peripheral blood mononuclear cells up to 8 weeks after the last dose of MK-8527 once monthly (3 mg, 6 mg, and 12 mg).	MK-8527-TP AUC _{0-last} , C _{trough} , C _{max} , and t _{1/2}
To explore the relationship between genetic variation and response to study intervention, and mechanisms of disease. Variation across the human genome may be analyzed for association with the pharmacokinetic and safety data collected in this study	Germline genetic variation and association to clinical data collected in this study

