4 STUDY DESIGN

4.1 Overall Design

This is a randomized, double-blind, placebo-controlled, parallel-group, multicenter study of oral MK-8527 administered QM in adults who are at low-risk of HIV-1 infection.

Approximately 350 participants will be randomized in a 2:2:2:1 ratio to 1 of 4 intervention groups: Group 1: MK-8527 (3 mg); Group 2: MK-8527 (6 mg); Group 3: MK-8527 (12 mg); and Group 4: Placebo. The screening window is 45 days and participants are allowed to rescreen 1 time (Section 8.11.1.2). The study population composition targets are: $\geq 30\%$ women, $\geq 30\%$ men, $\geq 80\%$ aged ≤ 35 years, and $\geq 30\%$ enrolled in Africa. Randomization will be stratified by sex (female, male) and region (Africa, non-Africa).

Participants will receive a total of 6 oral doses of the assigned blinded study intervention, 1 dose every 4 weeks, starting on Day 1. The final dose will be administered at the Week 20 visit. After the last dose, all participants will complete an 8-week blinded follow-up period.

The primary safety assessment will include all accumulated safety data during the intervention and follow-up period. AEs leading to discontinuation from study intervention will be assessed until Week 20 (last dose received). The Sponsor will perform an ongoing comprehensive review of safety parameters to assess for overall trends and outliers in reported AEs and event toxicities per standard monitoring procedures.

All participants will be evaluated for plasma MK-8527 PK drug levels, and a subset (approximately N=20 participants per intervention group) will be evaluated for MK-8527-TP in PBMC (PBMC Subset).

All participants and the investigators/clinical site personnel directly associated with study conduct will remain blinded to study intervention assignment through the 8-week follow-up period. The siDMC (internal) will be responsible for an interim safety review once 50% of the planned enrollment has reached Week 12 or discontinued from study intervention. Additional meetings of the siDMC may be triggered based on criteria outlined in the SAP/siDMC charter. An unblinded Sponsor team will review PK and safety data on an ongoing basis for the duration of the study. As per amendment 02, all Sponsor personnel except for a blinded medical monitoring team will be unblinded after the last expected Follow-up Week 4 visit, to enable earlier program strategic decision-making by the Sponsor.

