4.2.1.1 Safety Endpoints

The primary safety endpoints are the number of participants experiencing AEs and the number of participants discontinuing study intervention due to AEs. Safety evaluations will include physical examinations (including vital signs) and laboratory tests performed per the SoA (Section 1.3). AEs will be evaluated at each visit and assessed according to the guidelines in Section 8.4. Participants may be asked to return for unscheduled visits in order to perform additional safety monitoring.

Dose-dependent decreases in total lymphocyte and lymphocyte subset counts were observed in clinical studies with ISL, another investigational NRTI agent. The risk of lymphocyte decreases for MK-8527 at the proposed doses is considered low based on available nonclinical and clinical data. To further assess the risk, hematology with lymphocyte subset counts will be monitored, in conjunction with MK-8527 in plasma and MK-8527-TP in PBMC measurements to allow correlation with any dose-related effects.

In this study, criteria for discontinuation of study intervention for confirmed on-treatment decreases of total lymphocyte count <1000 cells/mm 3 or CD4+ T-cell count <500 cells/mm 3 are based on literature that identifies an increased frequency of infections or increased risk of infections when cell counts drop below these levels, whether caused by disease (eg, HIV infection, systemic lupus erythematosus, rheumatoid arthritis) or by disease-modifying drugs [Giovannoni, G., et al 2018] [Spiezia, A. L., et al 2022] [Merayo-Chalico, J., et al 2013] [Subesinghe, S., et al 2020] [Warny, M., et al 2018], and DAIDS criteria (Version 2.1, July 2017) [National Institute of Allergy and Infectious Diseases 2017]. In addition, discontinuation requires a confirmed $\geq 30\%$ decrease from baseline in either total lymphocytes or CD4+ T-cell counts (Table 3) so that participants whose baseline total lymphocyte counts or CD4+ T-cell counts are just above the discontinuation thresholds are

not discontinued for laboratory findings that are within the natural variability of these tests. A $\geq 30\%$ decrease was chosen based on published literature demonstrating that lymphocyte counts vary as much as 25% in healthy adults when measured as frequently as day-to-day and over longer periods of time (every 6 months for many years) [Aziz, N., et al 2019] [Aziz, N., et al 2019a] [Statland, B. E., et al 1978].

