#### **3.5.1.2 Statistical Methods for Safety Analyses**

There are no safety topics of special interest in this study.

Table 1 Analysis Strategy for Safety Parameters

Analysis Part	Safety Endpoint	Descriptive Statistics	95% Between-group CI
Overall Safety Assessment	Any AE	X	X
	Any serious AE	X	X
	Any drug-related AE	X	X
	Any Grade 3 to 4 AE	X	X
	Any serious and drug-related AE	X	X
	Any Grade 3 to 4 and drug-related AE	X	X
	Discontinued study intervention due to AE	X	X
	AE that resulted in death	X	X
	Specific AEs, SOCs, or PDLCs	X	
	Change from baseline results for laboratory values	X	

AE=adverse event; CI=Confidence Interval; PDLC=Pre-Defined Limit of Change; SOC=System Organ Class.

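### The SAP plans no estimate of lymphocyte change across dose or exposure, and only by-group description of laboratory change; a dose trend with a shape check would be a cheap addition

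*SAP*

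**What the plan says.** Protocol 2.3 gives the background: "Exposure/dose-dependent decreases in total lymphocyte and lymphocyte subset counts were observed in clinical studies with ISL". ISL is in the same class as MK-8527. For MK-8527 itself, Protocol 4.2.1.1 states: "The risk of lymphocyte decreases for MK-8527 at the proposed doses is considered low based on available nonclinical and clinical data". To assess that risk further, the same section monitors lymphocyte subsets together with plasma MK-8527 and MK-8527-TP in PBMC "to allow correlation with any dose-related effects".

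Protocol 2.1 says that the results will help to select the monthly dose for the efficacy studies, and Protocol 4.3 allows that dose to be interpolated from the three doses tested.

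On analysis, the SAP says:

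- SAP 3.5.1: "Safety analyses will be performed for the following between-group comparisons", followed by 3 mg, 6 mg and 12 mg, each against placebo.
- SAP Table 1 (3.5.1.2): the row "Change from baseline results for laboratory values" is marked for descriptive statistics and not for a 95% between-group CI. The same section says that there are no safety topics of special interest.
- SAP 3.6: one interim criterion uses the upper 95% bound of the treatment-minus-placebo difference in percent change in lymphocyte count.
- SAP 3.8.1, Table 2: power for that same difference, 100 against 50 participants.
- SAP 3.5.4: population PK modelling is left to a separate plan. Lymphocytes are not mentioned there.
- SAP 3.2: no hypotheses are tested.

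**The concern.** The reason given for collecting lymphocyte counts with drug levels is about dose, but the SAP has no analysis that uses the order of 0, 3, 6 and 12 mg or the measured exposure. Three separate contrasts with placebo also give no estimate at an untested dose, and the protocol leaves open that Phase 3 will use one.

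The planned handling of laboratory change is thinner still. The sample-size section is built around the lymphocyte difference from placebo and the interim criterion uses its confidence interval, yet the final-analysis table asks for no interval at all. Any dose-response or exposure-response estimate would then have to be devised after most Sponsor staff are unblinded and would count as post hoc.

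**Working it through.** **Inputs.** Allocation 100/100/100/50 (Protocol synopsis: about 350, ratio 2:2:2:1). Doses 0, 3, 6, 12 mg. SD of percent change 20 and a difference of 10 points (worked example in SAP 3.8.1). The alpha behind Table 2 is not stated; I assume two-sided 0.05. No dropout, as in Table 2. The documents give no dose-response shape, so I vary it.

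**1. The SAP's own figure.** SE = 20 × √(1/100 + 1/50) = 20 × √0.03 = 3.46. Noncentrality = 10/3.464 = 2.89, df 148. Power = 81.8%, which matches Table 2. This is a planning figure: Table 1 gives no between-group interval to which it would apply at the final analysis.

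**2. Linear slope on dose.** Mean dose = (50×0 + 100×3 + 100×6 + 100×12)/350 = 2100/350 = 6. Sxx = 50×36 + 100×9 + 100×0 + 100×36 = 6300. SE of slope = 20/√6300 = 0.252 per mg, so the SE of the implied 12 mg effect is 12 × 0.252 = 3.02. The 95% half-width is 1.96 × 3.02 = 5.93, against 1.96 × 3.464 = 6.79 pairwise.

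**3. What the slope compares.** Because the mean dose is 6, the 6 mg group has zero weight. The slope is (600·m12 − 300·m3 − 300·m0)/6300, where m0, m3 and m12 are the group means. The implied 12 mg effect is therefore (12×600/6300) × [m12 − (m0 + m3)/2] = 1.143 × [m12 − (m0 + m3)/2]. This explains why the gain depends on shape: the slope does well when 3 mg resembles placebo and badly when 3 mg resembles 12 mg.

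**4. Power by shape**, with a true fall of 10 points at 12 mg, SD 20, df 346:

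| Shape | True fall at 3 / 6 / 12 mg | Slope-implied fall at 12 mg | at 3 mg | Noncentrality | Power of trend |
|---|---|---|---|---|---|
| Linear | 2.5 / 5 / 10 | 1.143×8.75 = 10.0 | 2.5 | 3.31 | 91.0% |
| 12 mg only | 0 / 0 / 10 | 1.143×10 = 11.4 | 2.9 | 3.78 | 96.5% |
| Square root | 5 / 7.1 / 10 | 1.143×7.5 = 8.6 | 2.1 | 2.83 | 80.7% |
| Emax, ED50 3 mg | 6.25 / 8.3 / 10 | 1.143×6.875 = 7.9 | 2.0 | 2.60 | 73.6% |
| Flat | 10 / 10 / 10 | 1.143×5 = 5.7 | 1.4 | 1.89 | 47.0% |

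Noncentrality is the implied 12 mg fall divided by 3.02. The 12 mg versus placebo comparison has 81.8% in every row. With ordinal scores, the Emax case rises from 73.6% to 79.6%.

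**5. Sensitivity to the SD**, linear shape: at SD 25, 63.1% pairwise and 75.1% trend; at SD 30, 48.1% and 59.4%. At SD 20, the fall detectable with 80% power is 9.8 points pairwise and 8.5 by trend.

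**The case against.** The strongest reply is that this is a preference and not an error. The decline was seen with ISL, the MK-8527 risk is rated low, the primary endpoints are adverse events and discontinuations due to them, and by-dose summaries will show any ordering across groups. The protocol wording explains why the data are collected; it does not promise a model. All of this stands, and it is why the point is an improvement and not a defect. A reader might infer that the sponsor expects a lymphocyte effect of MK-8527 and has left its main safety question unanswered. The documents do not support that.

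A reader might also infer that the pairwise plan gives up power that a trend over all 350 would recover. That is not supported as a general statement. No hypotheses are tested, so precision is the better measure. The trend is better in two of the five shapes, level in one and worse in two. A lone slope also misstates effects when the shape is wrong: with a square-root response it implies 2.1 points at 3 mg where the truth is 5, and if only 12 mg acts it implies 2.9 where the truth is 0.

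The interim criteria concern individual intervention groups, so arm-specific estimates are needed in any case. Finally, the separate population PK plan might contain an exposure-response analysis. It was not available, and the SAP does not describe it as covering lymphocytes, so the matter is open and not settled either way.

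**Conclusion.** The point holds as a cheap improvement. The SAP contains no estimate of lymphocyte change across dose or exposure, although the protocol collects the data with that use in mind and may interpolate the Phase 3 dose. For laboratory change it plans only by-group description, which does not match its own power table or its interim criterion.

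If the response is linear, a trend cuts the standard error of the 12 mg effect by about 13% (3.02/3.46 = 0.87). The benefit is confined to responses that are roughly linear or concentrated at the top dose. These figures assume two-sided 0.05, a common SD of 20 and no dropout.

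**What to change.** In SAP 3.5.1 and Table 1, prespecify the following as estimation without hypothesis tests, for percent change from baseline in total lymphocytes and CD4+ T cells at a visit that the SAP names:

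- (a) Each dose minus placebo, with 95% CI. This brings Table 1 into line with Table 2 and the interim criterion.
- (b) In addition, a dose-trend estimate over 0/3/6/12 mg with 95% CI, adjusted for baseline, sex and region, with a prespecified shape check such as ordinal or Emax scores.
- (c) The correlation with plasma exposure, and with MK-8527-TP in the PBMC Subset (about 20 per group) as exploratory. If the population PK plan already covers this, a cross-reference is enough.

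The cost is a few added outputs from data already scheduled for collection. The downside is that the slope can understate effects at the lower doses when the response saturates, so (b) must be read beside (a) and not in its place.
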